5.3.2 Chemotherapy administration

5-Fluorouracil and cisplatin are commercially available antineoplastic agents. Investigators should use the approved package inserts of these drugs for complete prescribing information, including any special precautions.

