5.4.2.1 Dose modifications and treatment alterations for 5-FU

The dose of 5-FU will be modified, if the following toxicities (Table 3) are observed during the radiochemotherapy on the planned day of 5-FU infusion.

Once a 5-FU dose modification has occurred, the dosage may not be re-escalated for this patient. If therapy is delayed for longer than 2 weeks, the patient will be withdrawn from the study.

If on the day of planned 5-FU infusion one of the following toxicities occurs, a dose modification according to the following scheme will be performed:

Table 3: Dose modification for 5-FU in case of toxicities on the day of planned 5-FU infusion

Toxicity	CTC - Grade	Continue with Chemotherapy	Dose modification
Neutropenia	ANC $\geq 1.5 \times 10^9/L$	Yes	No
	ANC $< 1.5 \times 10^9/L$	Delay until ANC $\geq 1.5 \times 10^9/L$	No
	ANC $< 0.5 \times 10^9/L$	Delay until ANC $\geq 1.5 \times 10^9/L$	Yes 5-FU 75% of original dose
Thrombocytopenia	Platelets $\geq 100 \times 10^9/L$	Yes	No
	Platelets $< 100 \times 10^9/L$	Delay until platelets $\geq 100 \times 10^9/L$	No
	Platelets $< 25 \times 10^9/L$	Delay until platelets $\geq 100 \times 10^9/L$	Yes 5-FU 75% of original dose
Diarrhea	Grade 0-1	Yes	No
	Grade 2	Delay until resolved to grade < 2	No
	Grade 3	Delay until resolved to grade < 2	1 st occurrence: No 2 nd occurrence: Yes 5-FU 75% of original dose
	Grade 4	withdrawal	withdrawal
Mucositis/Stomatitis	Grade ≥ 1	Delay until resolved	Yes 5-FU 75% of original dose
Skin (except irradiated region and cetuximab-related skin toxicities)	Grade ≥ 2	Delay until grade 0-1	Yes 5-FU 75% of original dose
Further non-hematological toxicities (except nausea/vomiting and alopecia)	Grade 0-1	Yes	No
	Grade 2-3	Delay until grade 0-1	Yes 5-FU 75% of original dose
	Grade 4	withdrawal	withdrawal

If at any time during the radiochemotherapy one of the following toxicities occurs, a dose modification of 5-FU at the next planned infusion will be performed according to the following scheme:

Table 4: Dose modification for 5-FU in case of toxicities during radiochemotherapy

Toxicity	CTC-Grade	Dose modification
Neutropenia	ANC < 0.5 x 10 ⁹ /L	5-FU 75% of original dose
Thrombocytopenia	Platelets < 50 x10 ⁹ /l	5-FU 75% of original dose
Diarrhea	≥ Grad 3 (≥ stools/day or incontinence)	5-FU 75% of original dose
Nausea/vomiting	≥ Grad 3	5-FU 75% of original dose

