5.4.3 Cisplatin

5.4.3.1 Dose modifications and treatment alterations for cisplatin

Table 5: Dose modification regarding the cisplatin induced renal toxicity prior to every new course:

Creatinine value	Dose modification
≤ 1.5 mg/dl	no dose modification
> 1.5 mg/dl	Delay until creatinine is < 1.5 mg/dl, then restart with 50% of original dose

Additionally the following criteria have to be fulfilled prior to every chemotherapy course:

- Neutrophils ≥ 1,5 x 10⁹/L
- Thrombocytes ≥ 100 x 10⁹/L
- Diarrhea NCI-CTC Version 4.0 Grade < 2

If these parameters are not appropriately at the scheduled time point of the new course, cisplatin administration has to be discontinued until the criteria above will be fulfilled.

If cisplatin cannot be administered for less than two weeks, the therapy will be continued with the initial dosing.

If cisplatin cannot be administered for more than two weeks the administered dose will be 75% of the original value.

If at any time during the radiochemotherapy one of the following toxicities occurs, a dose modification of cisplatin at the next planned infusion will be performed according to the following scheme:

Table 6: Dose modification for cisplatin in case of toxicities during radiochemotherapy

Toxicity	CTC-Grade	Dose modification
Neutropenia	ANC < 0.5 x 10 ⁹ /L	Cisplatin 75% of original dose
Thrombocytopenia	Platelets < 25 x10 ⁹ /l	Cisplatin 75% of original dose
Further non-hematological toxicities (except nausea and vomiting)	Grade 3	Cisplatin 75% of original dose
	Grade 4	Discontinuation of chemotherapy

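### Tables 3 and 6 give different instructions for 5-FU after certain grade 4 mucositis or skin events, and the protocol does not say which applies (minor)

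*Combined protocol and SAP*

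**What the plan says.** Section 5.4.2.1 sets the 5-FU rules. Table 3 applies to toxicity present on a planned 5-FU day. Its mucositis entry is a single row: "Mucositis/Stomatitis Grade ≥ 1 Delay until resolved Yes 5-FU 75% of original dose". The skin row starts at grade 2, excludes the irradiated region and cetuximab-related reactions, and has the same pattern: wait for grade 0-1, then give 75%. Neither row has a grade 4 line. The diarrhea row and the row for further non-hematological toxicities do have one: "Grade 4 withdrawal withdrawal". The same section adds a limit on delay: "If therapy is delayed for longer than 2 weeks, the patient will be withdrawn from the study".

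Section 5.4.3.1 sets the cisplatin rules. Table 6 applies at any time during radiochemotherapy, and its lead-in says that "a dose modification of cisplatin at the next planned infusion will be performed". It has three rows: neutropenia, thrombocytopenia, and further non-hematological toxicities except nausea and vomiting. Every action cell names cisplatin except the grade 4 cell of the last row, which reads "Discontinuation of chemotherapy".

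Section 4.2.4 requires withdrawal from study treatment for grade 4 toxicity only when it is related to cetuximab.

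**The concern.** A patient with one of these grade 4 events on a planned 5-FU day falls under both tables. One lets 5-FU resume at a reduced dose once the event has cleared. The other appears to end it. Two of the roughly 15 centers could treat the same event in opposite ways, each following a written rule. Section 6.1.2 defines grade 4 as life-threatening or disabling, and section 5.1.2 names mucositis among the main reactions to 5-FU. What is at stake is therefore the clarity of a safety stopping rule.

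**Working it through.** The check is mainly a reading of the rules side by side, followed by a dose calculation.

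**1. Does each table reach the event?**
- Table 3: yes. Grade 4 lies inside *grade 1 or more* and *grade 2 or more*. The grade 4 withdrawal line for further non-hematological toxicities does not help, because mucositis and skin have rows of their own.
- Table 6: yes. Its other two rows are hematological and only nausea and vomiting are excluded, so mucositis and skin toxicity fall in the third row.
- Table 4 lists neither toxicity.

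**2. What does chemotherapy mean in the Table 6 cell?**
- *For both drugs:* section 5.3.2, on chemotherapy administration, opens "5-Fluorouracil and cisplatin are commercially available antineoplastic agents". Section 5.1.1.2 speaks of chemotherapy infusions directly after naming cisplatin and 5-FU. Section 6.1.2 lists stopping chemotherapy as one action, separate from actions on cetuximab. The neighbouring Table 6 cells say cisplatin where cisplatin is meant. The Table 3 column that holds the delay instruction is itself headed "Continue with Chemotherapy".
- *For cisplatin only:* the section heading, the table title and the lead-in.

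| Reading of the cell | Table 3 | Table 6 | Result |
|---|---|---|---|
| 5-FU and cisplatin | resume 5-FU at 75% | stop both | conflict |
| cisplatin only | resume 5-FU at 75% | stop cisplatin | no conflict, but 5-FU restarts after grade 4, unlike diarrhea |

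**3. Does another rule settle it?**
- Section 4.2.4 settles cetuximab-related grade 4 events, which can arise only in Arm A. It leaves every such event in Arm B, and unrelated events in Arm A.
- The 2-week limit settles slow recoveries only.
- Section 5.4.2 separates cetuximab from chemotherapy, not 5-FU from cisplatin.
- The adverse-event clause in section 4.2.4 is discretionary, and the reference to product information in section 5.1.2 is general. Neither ranks the tables.

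**4. Planned 5-FU at stake.** Inputs from section 4.1: four days per course, 1,000 mg/m²/day in courses 1-2 and 750 mg/m²/day in courses 3-4. The planned total is 2×4×1,000 + 2×4×750 = 14,000 mg/m². The event is taken as present on the first day of the course (Arm A days 36, 71, 99; Arm B days 29, 64, 92), with all remaining courses given. The difference is 75% of the remaining dose against none.

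| Event at | Remaining planned dose (mg/m²) | ×0.75 | Share of 14,000 |
|---|---|---|---|
| Course 2 | 4×1,000 + 2×4×750 = 10,000 | 7,500 | 53.6% |
| Course 3 | 2×4×750 = 6,000 | 4,500 | 32.1% |
| Course 4 | 4×750 = 3,000 | 2,250 | 16.1% |

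This takes 75% of each course's own planned dose. If the original dose means 1,000 mg/m²/day throughout, the figures are 750×12 = 9,000, 750×8 = 6,000 and 750×4 = 3,000. For a patient stopped at 45 Gy for surgery, 45/1.8 = 25 fractions. With a Monday start and no interruption, the last falls on radiotherapy day 33. Course 2 is due on radiotherapy day 29, so at most 4×1,000×0.75 = 3,000 mg/m² is in question.

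**The case against.** The strongest defence is that each drug has its own section. Read by heading, Table 6 governs cisplatin, Tables 3 and 4 govern 5-FU, and nothing conflicts. Restarting 5-FU at 75% after full resolution is then a design choice. This has weight. A reader might infer that the tables flatly contradict each other, and the documents do not support that with certainty. The defence still leaves unexplained why one cell says chemotherapy where the others say cisplatin. It also leaves Table 3 more lenient for grade 4 mucositis than for grade 4 diarrhea.

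A second objection concerns reach. A reader might infer that all grade 4 mucositis in Arm A is affected. It is not, because events related to cetuximab already lead to withdrawal under section 4.2.4. The remaining window is narrow: the event must be present on a planned 5-FU day and clear within 2 weeks, and Table 3 requires mucositis to be fully resolved. Investigators may also stop treatment whenever they think it necessary. All of this stands and limits the risk, but none of it chooses between the tables.

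Third, the span of radiochemotherapy is not fixed. The synopsis gives 6.5 to 7 weeks for the radio-immunochemotherapy, while section 6.2 speaks of every course of it. On the narrow reading, events at courses 3 and 4 may lie outside Table 6. The course 2 case, where most dose is at stake, is unaffected.

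**Conclusion.** The point holds as a minor inconsistency in a safety rule, with moderate confidence. It covers grade 4 mucositis or stomatitis not related to cetuximab (any such event in Arm B), and grade 4 skin toxicity outside the irradiated region and not related to cetuximab. The event must be present on a planned 5-FU day and resolve within 2 weeks (skin: to grade 0-1). On the more likely reading of Table 6 the two tables conflict. On the other reading, Table 3 departs from its own grade 4 rule for other toxicities. Either way the text needs clarifying.

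The size is at most 7,500, 4,500 or 2,250 mg/m² of planned 5-FU from course 2, 3 or 4, assuming 75% of each course's own dose and that all remaining courses are given. These are planned doses, not a measure of harm. A reader might infer a difference between arms or an effect on 2-year survival. The documents give no frequency for these events and show no such effect.

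**What to change.** - **Table 3:** limit the mucositis row to grades 1-3 and the skin row to grades 2-3. Add to each a grade 4 line ordering withdrawal, to match the existing diarrhea and further non-hematological rows.
- **Table 6:** reword the grade 4 cell to *Discontinuation of 5-FU and cisplatin*. State that where Table 3 orders withdrawal, that stricter action stands. Do not add a general rule that Table 6 prevails over Table 3: it would weaken the existing withdrawal rule for grade 4 diarrhea and other toxicities.
- **Follow-up:** state that withdrawn patients stay in survival follow-up.

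Rewording the cell to cisplatin alone would remove the conflict, but 5-FU would still restart after a grade 4 event.

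The cost is amendment wording in section 5.4, with no added patients, visits or procedures. The downside is that a few patients whose grade 4 event resolves quickly would lose further study treatment.

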5.5 Radiotherapy

The radiotherapy will be administered over 6.5 - 7 weeks, in 33 fractions of 1.8 Gy up to total dose of 59.4 Gy. 50,4 Gy will be administered to the loco-regional lymph nodes. If resectability has been achieved after 4-4.5 weeks (36-41.4 Gy), radiotherapy will be stopped at 45 Gy and patient will undergo surgery.

5.5.1 Technique and dosage of radiotherapy

Radiotherapy starts on the first day of the chemotherapy following cetuximab infusion and prior to the 5-FU and cisplatin infusions. A total of 59.4 Gy (at the reference point according to ICRU 62) will be delivered in daily fractions of 1.8 Gy for 6.5 - 7 consecutive weeks (5 fractions/week). Irradiation will be performed using high energetic photons, preferably a linear accelerator with photon energies of at least 6 MV. The 95% isodose should cover the target volume.

Isocentric 3- or 4- field techniques with individual absorbers will be used. To adequately perform planning a treatment simulator and computerized 3-D-treatment planning must be used. The CT-slices should be contiguous and not thicker than 10 mm, preferably 5 mm with clip labelling. Optimal patient positioning to reduce normal tissue damage - if necessary including the use of a belly board should be performed.

5.5.1 Adverse reactions and dose modifications of radiotherapy

Expected acute adverse reactions of the radiotherapy are esophagitis and dysphagia. These reactions may be aggravated by the concurrent chemotherapy. Treatment will be symptomatic. Generally, these acute adverse reactions abate within two to four weeks following completion of radiotherapy. In severe cases, the treatment may be interrupted for up to one week, if deemed necessary by the responsible radio-oncologist. If radiotherapy has to be stopped due to adverse reactions, the LKP has to be informed. Rare severe events are e.g.: skin reactions, pneumonitis, arrhythmia.

Interruption or termination of radiotherapy due to adverse reactions should be based on the following recommendations:

Table 7: Interruption of radiotherapy in case of gastrointestinal toxicity

Toxicity grade	esophagitis/dysphagia	Radiotherapy
0	none	continue
1	Mild dysphagia, but can eat regular diet	continue
2	Dysphagia requiring predominantly liquid, pureed or soft diet	Continue
3	Dysphagia, requiring feeding tube, IV hydration or hyperalimentation	Interruption of radiotherapy for a maximum of 7 days. If the esophagitis/dysphagia does not resolve, the radiotherapy should be stopped.
4	Complete obstruction (cannot swallow saliva); ulceration with bleeding not induced by minor trauma or abrasion or perforation	Stop radiotherapy

5.6 Prior and concomitant therapy

All concomitant medication or medication administered within the 4 weeks preceding study start and during the study must be recorded in the CRF. The generic name of the medication must be specified along with the duration of the treatment.

Additionally, any therapeutic, or surgical procedures performed during this study period should be recorded in the CRF, including the date, indication, description of the procedures, and any clinical findings.

Any change in the permitted concomitant medication being taken at the beginning of the clinical study must be recorded in the CRF, noting the type of medication, duration, and indication.

Additional concurrent chemotherapy of radiation therapy may not be administered. Sedatives, antibiotics, analgesics, antihistamines, steroids, Granulocyte-Colony-Stimulating Factor (G-CSF), erythropoietin or other medications as well as red blood cells, platelets or fresh frozen plasma transfusions may be given to assist in the management of pain, infection, and other complications of the malignancy. Patients must be premedicated with an antihistamine and a glucocorticoid prior to receiving the initial dose of cetuximab. Premedication with an antihistamine and a glucocorticoid is recommended prior to further subsequent weekly doses.

5.7 Other study conditions

Anything which may interfere with the immune systems of the patient should preferably be avoided except the indicated study regimen and necessary supportive treatment.

5.8 Treatment compliance

Since the intravenous infusion is administered in a hospital or in an outpatient setting, compliance can easily be supervised. Cetuximab, cisplatin and 5-FU will be administered either by the investigator or under his direct supervision.

The date and the exact amount of cetuximab given at each infusion will be documented in the CRF.

As a routine precaution, patients enrolled in this study will be observed from the start of the infusion until at least one hour after the end of the infusion in an area with resuscitation equipment and emergency agents (epinephrine, prednisolone equivalents etc.) available. In the event that the treatment has to be interrupted during infusion, the clinical staff should make an estimate of the percentage of dose received by the patient and document it in the CRF. Any reason for non-compliance should also be documented. Insufficient compliance is defined as a patient missing more than two infusions of cetuximab without medical reason. In the event of insufficient compliance, discontinuation of study treatment for this patient will be considered in mutual agreement between the investigator and the Investigator-Sponsor.

6 Assessment of safety

6.1 Adverse events

6.1.1 Definition of adverse event, adverse drug reaction and serious adverse event

6.1.1.1 Adverse events (or adverse experience) (AE)

An AE is any untoward medical occurrence in a patient or clinical investigation subject administered a pharmaceutical product and which does not necessarily have a causal relationship with this treatment.

An AE can therefore be any unfavorable and unintended sign (including an abnormal laboratory finding, for example), symptom, or disease temporally associated with the use of a medicinal product, whether or not considered related to the medicinal product.

Due to regulatory requirements, events occurring during pre- and post-treatment periods should also be designated as AEs. Therefore, safety surveillance - reporting of (S)AEs - commences at the time when the subject is enrolled into the study (date of signature of the informed consent) until the End of Study Visit has been performed. Therefore events occurring in the period between the signed informed consent and beginning of the study drug administration are to be designated as AEs. This procedure complies with requirements by some authorities.

6.1.1.2 Adverse drug reaction (ADR):

All noxious and unintended responses to a medicinal product related to any dose should be considered adverse drug reactions (ADRs).

The phrase "responses to a medicinal product" means that a causal relationship between a medicinal product and an AE is at least a reasonable possibility i.e. the relationship cannot be ruled out.

6.1.1.3 Serious adverse event or reaction/experience (SAE):

A serious AE (experience) or reaction is any untoward medical occurrence that at any dose:

- Results in death
- Is life-threatening

NOTE: The term "life-threatening" in the definition of "serious" refers to an event in which the subject was at risk of death at the time of the event; it does not refer to an event which hypothetically might have caused death if it were more severe.

- Requires in-patient hospitalization or prolongation of existing hospitalization
- Results in persistent or significant disability/incapacity
- Is a congenital anomaly/birth defect or
- Is an important medical event

Medical and scientific judgment should be exercised in deciding whether expedited reporting is appropriate in cases of important medical events that may not be immediately life-threatening or result in death or hospitalization but may jeopardize the subject or may require intervention to prevent one of the other outcomes listed in the definition above. These should also usually be considered serious.

Examples of such events are intensive treatment in an emergency room, or at home for allergic bronchospasm; blood dyscrasias or convulsions that do not result in hospitalization; or development of drug dependency or drug abuse, or malignant tumors when they are histologically different from the primary tumor.

6.1.1.4 Other events to be treated as SAEs

Exposure to drug during pregnancy/lactation.

In principle, pregnancy and the lactation period are exclusion criteria. In the event of a pregnancy occurring during the course of a study, the subject must be withdrawn from study drug immediately. The Investigator-Sponsor must be notified without delay and the subject followed during the entire course of the pregnancy and postpartum period. Parental and neonatal outcomes must be recorded even if they are completely normal and without AEs. The "Serious Adverse Event Form" (SAE report form) should be used, even though pregnancy is not considered a SAE. No "serious criterion box" should be checked. The SAE report form is solely used to ensure expedited reporting.

6.1.1.5 Events not to be treated as SAEs

Progression of disease is not to be regarded as a SAE.

Due to the seriousness of the disease in this study, certain conditions defined as SAEs will be excluded from expedited reporting on a SAE report form:

- Elective hospitalization and surgery for treatment of disease
- Elective hospitalization to simplify treatment or study procedures

6.1.2 Methods of recording and assessing adverse events

All AEs must be documented in the appropriate section of the CRF. For SAEs, a SAE report form (initial or follow up) must be completed in addition.

The following aspects must be recorded for each event in the CRF:

- A description of the AE in medical terms, not as reported by the subject;
- The date of onset (start date)
- The date of recovery (stop date)
- The grade as assessed by the investigator according to the definitions in NCI-CTC, Version 4.0.

Grade 1 = mild

Grade 2 = moderate

Grade 3 = severe

Grade 4 = life-threatening or disabling

Grade 5 = death related to AE

- The causal relationship to cetuximab or chemotherapy as assessed by the investigator; the decisive factor in the documentation is the temporal relation between the AE and the study drug. The following judgments of the causality to study drug or study procedures are to be used:

Not Related = There is not a temporal relationship to study drug administration (too early, too late, or study drug not taken), or there is a reasonable causal relationship between another drug, concurrent disease, or circumstance and the AE.

Not Likely = There is a temporal relationship to study drug administration, but there is not a reasonable causal relationship between the study drug and the AE,

Possible = There is a reasonable causal relationship between the study drug and the AE. Dechallenge information (information referring to withdrawal of drug) is lacking or unclear.

Probable = There is a reasonable causal relationship between the study drug and the AE. The event responds to dechallenge (withdrawal of study drug). Rechallenge is not required.

Certain/Definite = There is a reasonable causal relationship between the study drug and the AE. The event responds to dechallenge and recurs with rechallenge, when clinically feasible.

- Action taken on cetuximab (none, medication discontinued, dose reduction, medication delayed, reduction of infusion rate).
- Other action (none, concomitant medication given, new or prolonged hospitalization, procedural surgery, chemotherapy delayed, chemotherapy discontinued, chemotherapy dose reduction).
- The outcome according to the following definitions:
 - Recovered with sequelae.
 - Recovered without sequelae.
 - Ongoing, no therapy.
 - Ongoing, therapy.
 - Died.
 - Change in toxicity grade/severity.

- Seriousness: yes or no
- In case of SAEs it must be indicated whether the SAE is the leading event, i.e. the primary medical reason for SAE reporting.

If in any one subject the same AE occurs on several occasions, then the AE in question must be documented and assessed anew each time.

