4.2.4 Removal of patients from the study or study treatment

Patients are free to discontinue the study at any time without giving their reason(s).

The patient must be withdrawn from study treatment in the event of any of the following:

- Withdrawal of the patient's consent
- Occurrence of an exclusion criterion which is clinically relevant and affects the patient's safety
- Occurrence of AEs, if discontinuation is desired or considered necessary by the patient and/or investigator
- Occurrence of pregnancy during treatment
- Lack of subject compliance
- A delay of treatment with cetuximab for more than 2 consecutive weeks
- Occurrence of any grade 4 toxicities related to cetuximab
- Occurrence of \geq grade 3 allergic/hypersensitivity reaction related to cetuximab
- Occurrence of disease progression

If there is a medical reason for withdrawal, the patient will remain under the supervision of the investigator until the AEs have been resolved or declined to baseline values.

If a patient has failed to attend scheduled assessments in the study, the investigator must determine the reasons and circumstances as completely and accurately as possible.

In case of premature discontinuation of the study treatment by a patient, the investigations scheduled for the last visit should be performed, if possible. In any case, the CRF section entitled "End of Treatment" must be completed.

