6.1.3 Procedure for reporting serious adverse events

In the event of the occurrence of any clinical AE or abnormal laboratory test value that is serious or medically important during the course of the study or the post-treatment period, irrespective of the treatment received by the subject, the investigator is obliged to immediately inform the Investigator-Sponsor.

The immediate report by the investigator to the Investigator-Sponsor shall be followed by detailed, written reports using the SAE report form (for an “initial” SAE or for “follow-up” information on a previous SAE). The immediate and follow up reports shall identify subjects by unique code numbers assigned to the latter.

For names, addresses, telephone and fax numbers, see SAE report form.

The Investigator-Sponsor shall ensure that all reporting requirements according to the respective national law are followed. “Expectedness” to be assessed with regard to the valid IB for cetuximab. “Expectedness” with respect to a comparator or a concomitant anti-cancer treatment, if applicable, is to be assessed according to either the respective IB or versus the Product Information. A CIOMS-1 format shall be used for submitting expedited reports to the competent authorities, the ethics committee and to all investigators involved in this study according to all appropriate national and international laws. Where necessary, the CIOMS-1 form shall be accompanied by the relevant pages of the case report form.

Cetuximab **SUSARs** represent Serious Adverse Events related to cetuximab (=Adverse Reactions), considered “unexpected” with regard to the valid IB for cetuximab.

With respect to cetuximab, the Investigator-Sponsor shall only copy Merck in any cetuximab individual case safety report, which has been submitted expeditedly to the competent authorities. The report to Merck shall be sent via Fax only at the same time of reporting to the competent authorities.

The Investigator-Sponsor shall ensure that for a reported death of a subject, the investigator shall supply the Investigator-Sponsor and the Ethics Committee with any additional information as requested.

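### The causality categories in 6.1.2 overlap for events with two reasonable causes and conflict with the drug-reaction definition in 6.1.1.2, so cetuximab toxicity can be under-attributed inconsistently

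*Combined protocol and SAP*

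**What the plan says.** Section 6.1.1.2 defines an adverse drug reaction broadly. It is enough that "a causal relationship between a medicinal product and an AE is at least a reasonable possibility i.e. the relationship cannot be ruled out".

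Section 6.1.2 then gives the scale that investigators use. The item is introduced as "The causal relationship to cetuximab or chemotherapy as assessed by the investigator", and temporal relation is named as the decisive factor. The scale is introduced with "The following judgments of the causality to study drug or study procedures are to be used", but all five definitions refer to study drug only. *Not Related* applies if the timing does not fit, "or there is a reasonable causal relationship between another drug, concurrent disease, or circumstance and the AE". *Possible* begins "There is a reasonable causal relationship between the study drug and the AE. Dechallenge information" and adds that this dechallenge information is lacking or unclear.

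The action lists in 6.1.2 cover cetuximab and, under other actions, "chemotherapy delayed, chemotherapy discontinued, chemotherapy dose reduction". Neither list has an entry for radiotherapy.

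Three rules act on relatedness to cetuximab:
- Section 6.1.3: cetuximab SUSARs "represent Serious Adverse Events related to cetuximab (=Adverse Reactions") and must also be unexpected against the investigator's brochure.
- Section 4.2.4: one withdrawal trigger is "Occurrence of any grade 4 toxicities related to cetuximab".
- Section 5.4.1.1: cetuximab dose adjustment is limited to grade 3 skin toxicity attributed to cetuximab.

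**The concern.** The second condition for *Not Related* asks only whether something else is a reasonable cause. It does not ask whether the study drug has been excluded. Section 6.1.1.2 asks the opposite question: can the drug be ruled out? An event that could come from either source gets different answers in the two sections, and it also fits two categories of the scale itself. No rule says which prevails.

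This matters because Arm A gives cetuximab together with cisplatin, 5-FU and radiotherapy, so a second reasonable cause is often available. Two centres could code the same event in opposite ways and both comply. Where the protocol acts on relatedness to cetuximab, the consequence would then depend on which category the investigator chose.

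**Working it through.** The plan states no figure on this point, so the check is of wording, plus one count.

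**Test event.** Take severe neutropenia in Arm A after the first chemotherapy course. Section 5.3.1 describes a raised risk of this when cetuximab is combined with platinum, so both drugs are reasonable causes.

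| Definition | What it asks | Met? |
|---|---|---|
| *Not Related*, first condition (6.1.2) | Timing does not fit | No |
| *Not Related*, second condition (6.1.2) | Another cause is reasonable | Yes (cisplatin) |
| *Possible* (6.1.2), if dechallenge information is lacking | Study drug is a reasonable cause | Yes (cetuximab) |
| Adverse drug reaction (6.1.1.2) | Relationship cannot be ruled out | Yes |

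The event meets two opposite categories, and one of them contradicts 6.1.1.2. With clear dechallenge information, the same overlap arises with *Probable*.

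**Meaning of study drug.** The item names cetuximab or chemotherapy, so two readings are open.
- If study drug means cetuximab, cisplatin and 5-FU count as another drug and the overlap above applies.
- If it means cetuximab and chemotherapy together, cisplatin is no longer another drug. But the text then requires no judgement specific to cetuximab, which 6.1.3, 4.2.4 and 5.4.1.1 need. Radiotherapy or concurrent disease can still trigger the second condition.

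**How often a second cause is available.** Section 5.4.1 gives 14 weekly infusions, which fall on days 1, 8, ..., 1 + 7 × 13 = 92. Arm A chemotherapy starts on day 8 (4.1), and radiotherapy starts on the first chemotherapy day (5.5.1, technique and dosage). Infusions on or after day 8 number 14 − 1 = 13. Only days 1 to 7 are cetuximab alone.

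**Which rules use the answer.**

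| Rule | Depends on attribution to cetuximab? |
|---|---|
| SUSAR classification (6.1.3) | Yes, and on unexpectedness |
| Grade 4 withdrawal trigger (4.2.4) | Yes |
| Skin dose adjustment (5.4.1.1) | Yes |
| Hypersensitivity of grade 3 or above | Yes in 4.2.4; the re-treatment text in 5.4.1.2 does not repeat the condition |
| SAE notification to the sponsor (6.1.3) | No |
| AE follow-up to the End of Study Visit (6.1.4) | No |
| Six-week follow-up extension (6.1.4) | No; it turns on relation to study treatment |
| DSMB parameters (10) | No |
| Toxicity comparison between arms (8.3.1) | No |

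**Radiotherapy.** It is protocol treatment, and the second section numbered 5.5.1 lists its own adverse reactions. Table 7 makes interruption or stopping a response to oesophagitis. Yet radiotherapy is absent from the named agents, the five definitions and both action lists. The phrase about study procedures in 6.1.2 could be read to include it, but no definition follows that up.

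**The case against.** The strongest reply is that the overlap does not dictate the lower category. An investigator who thinks cetuximab contributed can code *Possible* and be fully compliant. Other text pulls that way: 6.1.2 calls temporal relation decisive, which with weekly cetuximab favours attribution, and 5.4.2 exempts cetuximab from modification only for toxicities due to chemotherapy alone, so shared causation is contemplated. This stands. A reader might infer that the scale turns every two-cause event into *Not Related*; the documents do not support that. But neither passage says which category prevails, so the conflict remains.

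The consequences are also bounded. A SUSAR must be unexpected against a brochure that is not among the documents, and several likely examples (neutropenia with infection, hypocalcaemia, cardiovascular events) are already described in 5.3.1 as known risks. Section 4.2.4 separately provides for withdrawal whenever the patient or investigator considers it necessary because of an adverse event. Both points stand and narrow the effect.

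A reader might also infer that the trial's main safety comparison is compromised, for instance by pointing to the 16% versus 0% grade 3/4 diarrhoea in the randomised chemotherapy trial cited in 2.3.2.1. That is a contrast between arms. This trial's own between-arm comparison does not use attribution, so it would show such a difference however the events were coded.

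Finally, a reader might conclude that radiotherapy interruptions go unrecorded. The missing action code is real. But the second 5.5.1 requires the coordinating investigator to be told when radiotherapy is stopped for adverse reactions, and the CRF is not available to check. Loss of that information is not shown.

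**Conclusion.** The point holds as a defect of definition. Sections 6.1.2 and 6.1.1.2 conflict for any event with two reasonable causes, and within 6.1.2 the categories are not mutually exclusive. This permits inconsistent under-attribution to cetuximab in SUSAR classification of unexpected events, the grade 4 withdrawal trigger and the skin-toxicity rule. Under-attribution is a plausible direction, not a demonstrated result, and its size cannot be computed from the documents. The count of 13 of 14 infusions shows only that a second treatment is present for most of Arm A treatment; it is not an error rate.

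The conclusion assumes that *Possible* or higher counts as related, which is the natural reading of 6.1.1.2. It does not extend to the between-arm safety comparison, DSMB monitoring or SAE notification. It extends to follow-up only for an event judged unrelated to every study treatment, which would lose the six-week extension.

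**What to change.** - Reconcile 6.1.2 with 6.1.1.2 and make the categories mutually exclusive. An alternative cause should give *Not Related* only if a contribution of the study treatment can be ruled out; if both are reasonable, the category is at least *Possible*.
- Record causality separately for cetuximab, chemotherapy and radiotherapy, so that the rules tied to cetuximab have a judgement specific to it.
- Add an action code for radiotherapy interrupted or stopped.

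No clinical management rule changes.

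The cost is a wording amendment, additional causality fields and one action code. Somewhat more events will count as related, and some may need expedited reporting. Timing adds a cost: 8.4 reports 66 treated patients by the end of July against an expected Full Analysis Set of 72 to 78, that is 66/78 = 85% to 66/72 = 92%. Events already coded would have to be re-assessed under the new wording, or the report must state that two definitions were used and which events fall under each.
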